## STATISTICAL ANALYSES

### SAMPLE SIZE

We performed a sample size analysis to determine how many patients are needed to be able to detect the minimal clinically important difference in shoulder external/internal rotation, which is between 14° and 22°. We used 80% power and a significance level of 0.05, and based on a review of the literature, we expect a standard deviation between 8° and 18°. Table I illustrates for each effect size, the minimum detectable difference with a standard deviation of 8° and of 18°. Using a sample size of 35 per group (effect size = 0.68), we would be able to detect between 5.4° and 12.2° difference, which will be sufficient to detect a clinically important difference.

**Table I.** Varying effect size and sample size for 80% power and  $\alpha=0.05$ , and the minimum detectable differences with a standard deviation of both 8 and 18.

Effect Size	Total N	n Per Group	Standard Deviation	Minimum Detectable Difference	Standard Deviation	Minimum Detectable Difference
0.55	106	53	18	9.9	8	4.4
0.60	89	45	18	10.8	8	4.8
0.64	80	40	18	11.52	8	5.12
0.65	76	38	18	11.7	8	5.2
0.68	70	35	18	12.2	8	5.4
0.7	66	33	18	12.6	8	5.6
0.75	58	29	18	13.5	8	6
0.8	51	26	18	14.4	8	6.4

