## OBJECTIVE

- The primary objective of this study is to determine whether external rotation and internal rotation two years postoperatively is impacted by humeral component version in reverse shoulder arthroplasty
- The secondary objective is to determine whether functional outcomes two years postoperatively are impacted by humeral component version in reverse shoulder arthroplasty

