## HYPOTHESIS

- Patients that receive RTSA with the humeral component positioned in 30 degrees of retroversion will have greater external rotation and worse internal rotation postoperatively than those that have 0 degrees of version.
- Patients that receive RTSA with the humeral component positioned in 0 degrees of version will have higher functional outcomes scores, due to improved internal rotation, than those that have 30 degrees of retroversion.

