## RANDOMIZATION

The 85 patients enrolled in the study will be randomized in a 1:1 ratio to have their procedure performed either with a humeral component positioned in 0 degrees of version or 30

degrees of retroversion. Randomization assignments will be contained in sequentially numbered, opaque, sealed envelopes, which will be prepared by a statistician in the research institute. After the patient is consented, they will be assigned to a group following the treatment listed in the envelope. Key personnel not collecting data will perform randomization and inform the surgeon of the group in order to keep data collection blinded. The patient will also remain blinded to their assignment. Logs will be maintained by the randomizing personnel.

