## DATA COLLECTION

Baseline data will be collected before the patient's procedure, after consent has been signed. Patients will be followed at standard-of-care follow-up appointments in the clinic at 3 months, 6 months, one year, and two years postoperatively. To help prevent dropouts, follow-up requirements will be discussed with the patient before consent and all patients will be called as each time point approaches to schedule follow-up appointments. At each appointment the patient will complete patient-reported outcomes questionnaires and will undergo a physical exam with a clinical research coordinator blinded to the patient's study group. Standard-of-care x-ray images will also be assessed.

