### DATA ANALYSIS

The range-of-motion, strength measures, patient-reported outcomes scores, and patient demographic factors will be compared between the two treatment groups. A table of descriptive summaries by treatment group will be prepared (means and standard deviations if normally distributed, median and range if not normally distributed, counts and percentages for categorical variables). Confidence intervals for the means/medians for each of the two groups will also be computed. The change from baseline as well as the absolute postoperative outcomes measurements will be used for comparison. Before comparing continuous variables, data sets will be assessed for normality using a Shapiro-Wilk Test. For normal data, an independent student's t-test will be used to compare means. A Mann-Whitney Rank Sum Test will be used for data that is ordinal or not normally distributed. The two treatment groups will be compared on categorical variables using the Fisher's Exact test.

Missing data will not be imputed, but the number of data points available at each time point postoperatively will be clearly reported in publications. For all tests, a p-value  $< 0.05$  will be considered statistically significant. A Bonferroni correction will be used to account for repeated measures and control for a Type I error. Graduate-trained engineers will analyze data with SPSS statistical software (SPSS Version 22.0, IBM, Inc).

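### The power statement uses an unadjusted 0.05, but the analysis plan adds a Bonferroni correction without giving its divisor, its reach to the two-year tests, or a primary scale

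*Combined protocol and SAP*

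**What the plan says.** **Primary question.** The Objective section reads "The primary objective of this study is to determine whether external rotation and internal rotation two years postoperatively is impacted" by humeral component version, so there are two primary outcomes at one time point. The Hypothesis section predicts that the 30° group "will have greater external rotation and worse internal rotation postoperatively than those that have 0 degrees of version". It does not say whether one of these results is enough or both are needed.

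**Sizing.** The Sample Size section states: "We used 80% power and a significance level of 0.05". Table I uses the same alpha and mentions no adjustment. For 35 per group the section concludes: "we would be able to detect between 5.4° and 12.2° difference, which will be sufficient to detect a clinically important difference". The important difference is given as 14° to 22° and the SD as 8° to 18°.

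**Analysis.** The Data Analysis section sets p < 0.05 as the threshold for every test and adds: "A Bonferroni correction will be used to account for repeated measures and control for a Type I error". On the scale it says: "The change from baseline as well as the absolute postoperative outcomes measurements will be used for comparison". Neither scale is named as primary.

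**Visits and numbers.** The Data Collection section has patients seen "in the clinic at 3 months, 6 months, one year, and two years postoperatively", which makes four postoperative visits. The Randomization section says: "The 85 patients enrolled in the study will be randomized in a 1:1 ratio". No dropout rate is given, and missing data are not imputed.

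**The concern.** A Bonferroni correction divides alpha by the number of tests, so it is not a complete rule until that number is given. The plan gives the purpose of the correction. It does not give the divisor, say whether the two-year rotation tests are among those corrected, or say whether 0.05 applies to adjusted or unadjusted p-values.

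Two things are at stake. First, the stated power may not describe the planned analysis: Table I is built on 0.05, and any correction that reaches the two-year tests lowers that. Second, the primary result could be read in more than one way. A two-year p-value of 0.03 would be positive with no correction and negative with a divisor of 2 or more. With two scales also open, the choice could be made after the data are seen.

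**Working it through.** **Inputs.** From Sample Size: 35 per group, effect size d = 0.68, power 80%, alpha 0.05, SD 8° to 18°, smallest important difference 14°. From Randomization: 85 enrolled, 1:1. From Data Collection: four postoperative visits. Assumed: two-sided tests (not stated, but only two-sided testing reproduces the plan's 35; one-sided gives 28), a t-test on the measured angle, and every divisor m, since the plan gives none.

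**Formulas.** Each test is at alpha = 0.05/m. Power comes from the noncentral t distribution with 2n − 2 degrees of freedom and noncentrality d × √(n/2). The detectable difference is the d that gives 80% power, multiplied by the SD.

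**Step 1: the plan's own figure.** With d = 0.68 and n = 35, the noncentrality is 0.68 × √17.5 = 2.84 and power at 0.05 is 80.1%. Then 0.68 × 8 = 5.4° and 0.68 × 18 = 12.2°. All eight sample sizes in Table I reproduce. The table is correct for a single test at 0.05.

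**Step 2: the same 35 per group with a correction.** For 14° at SD 18°, d = 14/18 = 0.778.

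| Divisor m | Alpha per test | Power at d = 0.68 | Detectable d at 80% power | In degrees, SD 8° to 18° | Power for 14° at SD 18° |
|---|---|---|---|---|---|
| 1 (two-year tests not corrected) | 0.05 | 80.1% | 0.679 | 5.4°–12.2° | 89% |
| 2 (two rotations) | 0.025 | 70.9% | 0.751 | 6.0°–13.5° | 83% |
| 4 (four visits) | 0.0125 | 61.1% | 0.817 | 6.5°–14.7° | 75% |

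**Step 3: where the 14° conclusion stops holding.** The largest SD at which 14° is detectable with 80% power is 14 divided by the detectable d. For m = 2 this is 14/0.751 = 18.6°, above the whole stated range. For m = 4 it is 14/0.817 = 17.1°, just inside the range. At SD 18° and m = 4, 80% power for 14° needs 39 per group (80.7%), or 78 analysed.

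**Step 4: all 85 analysed (42 and 43).** With m = 2, power at d = 0.68 is 80.1% and the SD 18° figure is 12.2°, so the stated claim just holds. With m = 4, power at d = 0.68 is 72% and the SD 18° figure is 13.3°; power for 14° at SD 18° is 85%.

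**Step 5: the two-year tests spared.** External and internal rotation are then each tested at 0.05. If either counts as success, the chance of at least one false positive is 1 − 0.95² = 9.75% when the two are uncorrelated. From the bivariate normal it is 9.1% at correlation 0.5 and 7.8% at 0.8. The correlations are assumptions.

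**Step 6: both rotations required.** Each can be tested at 0.05 with no alpha split, but the joint power is lower. At 35 per group and zero correlation it is 0.801² = 64% at d = 0.68 and 0.894² = 80% for 14° at SD 18°. At correlation 0.8 in the hypothesised directions, simulation gives 73% and 85%. Whatever the correlation, it cannot fall below 2 × 0.801 − 1 = 60% and 2 × 0.894 − 1 = 79%.

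**The case against.** The best defence has four parts.

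1. **The purpose of the correction is stated.** Repeated measures, read with the visit schedule, points to the four visits. This is fair, and it would be too strong to say the plan gives no idea of the family. But under that reading the two-year tests are at 0.0125, and the 80% power statement no longer describes the analysis.

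2. **The target is 14° to 22°, not 5.4°–12.2°.** This also stands. A reader might infer that the trial is too small for a clinically important difference. The plan's figures do not support that: the shortfall needs a divisor of at least 4, an SD near its maximum, a true difference near 14°, and about 35 per group analysed.

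3. **85 patients are enrolled, not 70.** With 78 or more analysed, the 14° conclusion survives a divisor of 4. However, the power statement is made for 35 per group, and no expected dropout rate says which number will apply.

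4. **A four-visit correction already protects the two-year pair.** It does: with each rotation at 0.0125, the chance of a false positive in that pair is 2.1%–2.5% (correlation 0.8 to 0). The absence of a separate correction between rotations is therefore not a real fault under that reading. A divisor of 8 (visits and rotations) would give worse figures, but the stated purpose does not mention correcting across outcomes, so that reading has little support.

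**Conclusion.** The point holds as a mismatch between the stated power and the stated analysis, together with a gap in specification. The divisor, the reach of the correction to the two-year tests and the primary scale are all left open, and neither natural reading leaves the plan complete:

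- **Correction over four visits:** at 35 per group the plan has 61% power at effect size 0.68 and detects 6.5°–14.7°, against the stated 80% and 5.4°–12.2°.
- **Two-year tests not corrected:** Table I is right, but the error rate for the two primary rotations is 7.8%–9.8% if either counts as success.

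The plan should be corrected on this, but it is not a fatal flaw. Table I contains no arithmetic error, and a divisor of 2 leaves 14° detectable over the whole stated SD range. The gap in the text is certain. The sizes above rest on assumed divisors and correlations, two-sided t-tests, and the plan's own SD range.

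**What to change.** **Preferred.** Name external and internal rotation at two years, on one stated scale, as the primary family. Apply Bonferroni or Holm to the two tests, size each at 0.025, and make the earlier visits and the other scale supportive. Say whether 0.05 refers to adjusted p-values. Restate the detectable difference at 35 per group as 6.0°–13.5°.

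**If the four-visit correction is kept.** State the divisor of 4, restate the detectable difference as 6.5°–14.7°, and qualify the claim of sufficiency for an SD above about 17.1° unless at least 39 per group are analysed.

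**If both rotations must be shown.** Say so, test each at 0.05, and report the joint power (64%–73% at effect size 0.68 and 80%–85% for 14° at SD 18°, for assumed correlations of 0 to 0.8).

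**Cost.** A few sentences in the statistical section. The preferred option needs no extra patients; its downside is a slightly less favourable stated figure, 13.5° instead of 12.2° at SD 18°, which is still below 14°. Requiring both rotations would mean stating a joint power below 80% for the 5.4°–12.2° range.

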### DATA ANALYSIS

The range-of-motion, strength measures, patient-reported outcomes scores, and patient demographic factors will be compared between the two treatment groups. A table of descriptive summaries by treatment group will be prepared (means and standard deviations if normally distributed, median and range if not normally distributed, counts and percentages for categorical variables). Confidence intervals for the means/medians for each of the two groups will also be computed. The change from baseline as well as the absolute postoperative outcomes measurements will be used for comparison. Before comparing continuous variables, data sets will be assessed for normality using a Shapiro-Wilk Test. For normal data, an independent student's t-test will be used to compare means. A Mann-Whitney Rank Sum Test will be used for data that is ordinal or not normally distributed. The two treatment groups will be compared on categorical variables using the Fisher's Exact test.

Missing data will not be imputed, but the number of data points available at each time point postoperatively will be clearly reported in publications. For all tests, a p-value  $< 0.05$  will be considered statistically significant. A Bonferroni correction will be used to account for repeated measures and control for a Type I error. Graduate-trained engineers will analyze data with SPSS statistical software (SPSS Version 22.0, IBM, Inc).

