## SCHEDULE OF EVENTS

Study Procedure	Preoperative	Surgery	3 months	6 months	1 year	2 years
Visit Window	8 wks to surgery	N/A	± 4 weeks	± 6 weeks	± 2 months	± 4 months
Review inclusion and exclusion criteria	X					
Informed consent review and signature	X					
Study group determination (randomization)	X*					
Intervention		X				
Patient-reported outcomes questionnaires (ASES, WOOS, PROMIS, VAS)	X*		X	X	X	X
Physical exam (range-of-motion and strength)	X*		X	X	X	X
Standard-of-care x-rays	X*		X	X	X	X

Assess for adverse events	X*	X	X	X	X	X
---------------------------	----	---	---	---	---	---

\*Consent will happen before any study procedures or assessment are done and randomization will occur at that time

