## APPENDIX A

Research Assessment Form

MOTION	Left Shoulder	Right Shoulder				
Abduction:	_____ degrees	_____ degrees				
Forward Flexion:	_____ degrees	_____ degrees				
External Rotation:	_____ degrees	_____ degrees				
	 Hand Behind Head, Elbow Forward	 Hand Behind Head, Elbow Forward				
	 Hand Behind Head, Elbow Back	 Hand Behind Head, Elbow Back				
	 Hand to top of Head, Elbow Forward	 Hand to top of Head, Elbow Forward				
	 Hand to top of Head, Elbow Back	 Hand to top of Head, Elbow Back				
	 Full Elevation	 Full Elevation				
Internal Rotation:	_____ degrees	_____ degrees				
	 Lateral Thigh	 Lateral Thigh				
	 Buttock	 Buttock				
	 Lumbosacral Junction	 Lumbosacral Junction				
	 Waist (L3)	 Waist (L3)				
	 T12 Vertebra	 T12 Vertebra				
	 Interscapular (T7)	 Interscapular (T7)				
STRENGTH (N or lbs)						
Abduction	_____	_____	_____			
Forward Flexion	_____	_____	_____			
Internal Rotation	_____	_____	_____			
External Rotation	_____	_____	_____			
Drop Arm?	Positive	Negative	Positive	Negative		
Belly Press?	Positive	Negative	Positive	Negative		
Lift-Off?	Positive	Negative	Positive	Negative		
External Rotation Lag?	Positive	Negative	Positive	Negative		
Is testing affected by pain?	Yes	No	Yes	No		
Neural Deficits?	Motor	Sensory	None	Motor	Sensory	None

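### Two unranked, unadjusted tests (change and absolute value) answer each rotation question, where one baseline-adjusted ANCOVA would give a single and usually more precise answer

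*Combined protocol and SAP*

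**What the plan says.** The Objective section sets one question for each rotation: whether "external rotation and internal rotation two years postoperatively is impacted by humeral component version". The Data Analysis section then gives two scales for answering it: "The change from baseline as well as the absolute postoperative outcomes measurements will be used for comparison". Normally distributed data go to an independent t-test. For the rest, "A Mann-Whitney Rank Sum Test will be used for data that is ordinal or not normally distributed". No baseline-adjusted model appears anywhere in the document.

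On multiplicity, the same section says "A Bonferroni correction will be used to account for repeated measures and control for a Type I error". It gives no family and no divisor.

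Baseline values will be available. Data Collection places the baseline assessment before surgery, and the Schedule of Events lists motion, strength and all questionnaires preoperatively.

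The Sample Size section relies on 35 per group and an effect size of 0.68, with an SD of 8° to 18°. It does not say whether that SD belongs to the absolute value or to the change.

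**The concern.** The two scales are different estimators of the same treatment effect. Under randomization both are unbiased, but they differ in variance and will not always agree on significance. With no scale ranked first, nothing fixes which result answers the primary objective, and the choice could be made after the data are seen.

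The Bonferroni sentence can be read two ways, and each has a cost. If the pair is outside the correction, the second test adds false positives. If it is inside, alpha is spent on a near-duplicate of the first test.

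Both tests also leave the baseline measurement underused. The absolute-value test ignores it, and the change score subtracts it with a fixed slope of 1. ANCOVA estimates the slope, so it is the more precise analysis unless the correlation is near 0 or the true slope is near 1.

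**Working it through.** **Inputs from the Sample Size section:** 35 per group, effect size 0.68, alpha 0.05 (two-sided reproduces Table I), 80% power, SD 8° to 18°, clinically important difference 14° to 22°.

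**Assumptions:** correlation r between preoperative and two-year values of 0.2, 0.4 or 0.6 (the documents give none); the stated SD is that of the absolute value; baseline and follow-up SDs equal unless noted; normal data.

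**Step 1. The plan's own figure.** Noncentral t, 35 per group: power for 0.68 SD is 80.1%. The detectable difference at 80% power is 0.679 SD, so 0.679 × 8 = 5.4° and 0.679 × 18 = 12.2°. The stated sample size reproduces.

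**Step 2. Precision.** Variance relative to the absolute-value test:

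- Change: 1 + k² − 2rk, where k is baseline SD divided by follow-up SD. At k = 1 this is 2(1 − r).
- ANCOVA: (1 − r²)(1 + 1/66), with 67 degrees of freedom. The second factor is the cost of estimating the slope.

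The detectable difference is approximately the absolute-value figure times the square root of the factor.

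| r | Change factor | ANCOVA factor | SD 18°: absolute / change / ANCOVA | SD 8°: absolute / change / ANCOVA |
|---|---|---|---|---|
| 0.2 | 1.60 | 0.975 | 12.2° / 15.5° / 12.1° | 5.4° / 6.9° / 5.4° |
| 0.4 | 1.20 | 0.853 | 12.2° / 13.4° / 11.3° | 5.4° / 6.0° / 5.0° |
| 0.6 | 0.80 | 0.650 | 12.2° / 10.9° / 9.9° | 5.4° / 4.9° / 4.4° |

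ANCOVA breaks even with the absolute value at r² = 1/67, that is r = 0.12. At r = 0 it is about 0.1° worse at SD 18°. With unequal SDs (SD 18°, r = 0.4), the change score gives 11.8° at k = 0.7 and 15.7° at k = 1.3; ANCOVA stays at 11.3°.

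**Step 3. Disagreement.** Simulation, 200,000 trials per r, true difference 0.68 SD, each test at 0.05. Power is 80% for the absolute value, 60%/73%/88% for change and 81%/86%/94% for ANCOVA. The first two disagree on significance in 29%/25%/21% of trials.

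**Step 4. Pair not covered by Bonferroni.** Under the null, at least one of the two tests is significant at 0.05 in 8.8%/8.9%/9.1% of trials. For external and internal rotation together, treated as independent, this is 1 − (1 − 0.089)² = 17%, against 1 − 0.95² = 10% on one scale.

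**Step 5. Pair covered.** At 0.025 each, the rate is 4.5% to 4.7%. Power for 0.68 SD on the absolute value is:

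| Alpha per test | Divisor | Power |
|---|---|---|
| 0.05 | 1 | 80% |
| 0.025 | 2 (two scales) | 71% |
| 0.0125 | 4 (four visits) | 61% |
| 0.00625 | 8 (visits and scales) | 51% |

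**Step 6. At the 14° threshold, SD 18°.** The absolute-value test has 89% power at 0.05 and 75% at 0.0125. ANCOVA at 0.0125 has 76%/83%/93%.

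**The case against.** Five points can be made for the plan.

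- **The text leans towards the absolute value.** The Objective and Hypothesis sections speak of rotation after surgery, which reads most naturally as the postoperative level. That is fair, but Data Analysis expressly uses both scales, so the lean does not settle the choice.
- **0.68 SD is a hard case.** At SD 18° it is 12.2°, below the plan's own 14°. For a 14° difference, the absolute-value test at 0.025 keeps 83% power at SD 18° and 98% at SD 13°. Disagreement at r = 0.2/0.4/0.6 falls to about 23% to 24%/17%/12% at SD 18°, 6%/2%/1% at SD 13° and about zero at SD 8°. These figures stand. The cost is material mainly towards the upper end of the SD range, but 0.68 SD is the effect on which the plan bases its sample size.
- **Bonferroni may already suffice.** A divisor of four for the visits would hold external and internal rotation on both scales at two years to 4.5% to 4.7%. That is correct, so the 9% and 17% apply only where the two-year tests go uncorrected. The 17% also treats the two rotations as independent.
- **ANCOVA is an efficiency choice.** The planned tests are valid, and the gain depends on r. Eligibility requires external rotation beyond neutral, which restricts baseline range and could lower r for that outcome. This stands: at r = 0.2 the gain is only about 0.1° over the absolute-value test.
- **Naming one scale would be enough.** It would remove the duplication, but it would forgo the usual precision gain and require a choice between two estimators whose ranking depends on an unknown r.

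**Conclusion.** The concern holds. For each rotation at two years the plan has two unadjusted tests, no primary scale, and a multiplicity rule whose reach over the pair is unstated. At 35 per group and the plan's design effect, the tests disagree in roughly a fifth to three tenths of trials. Depending on how Bonferroni is read, the duplication either raises the error rate for one outcome at one visit to about 9% or costs about 9 points of power.

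The scale also matters for the claim that 35 per group is sufficient. At SD 18° and r = 0.2, the change score can detect only 15.5°, above the 14° lower limit, while ANCOVA stays below 14° at every r examined.

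These sizes rest on an assumed r of 0.2 to 0.6, normal data, and reading the stated SD as that of absolute values. The ambiguity over which test counts does not depend on r; the precision gain does, and it is negligible at r = 0.2. The stated sample size calculation is not in error.

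**What to change.** - **Primary analysis:** for external and internal rotation in degrees at two years, fit an ANCOVA of the two-year value on treatment group, with the preoperative value of the same measure as covariate. Report the adjusted difference with a 95% confidence interval.
- **Other continuous outcomes:** use the same model for strength and continuous questionnaire scores.
- **Non-normality:** if residuals are clearly non-normal, add ANCOVA on ranks or a bootstrap interval as a sensitivity analysis.
- **Raw and change values:** report them descriptively, without tests.
- **Ordinal and categorical outcomes:** keep a rank-based or ordinal method for the anatomical internal-rotation levels in Appendix A, and Fisher's exact test for the clinical signs.

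This removes only the duplication of scales. Multiplicity across the two rotations and the visits remains, and needs a stated Bonferroni family and divisor.

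The cost is a change of wording, made before any group comparison is run, and one degree of freedom per model. Baseline values are already to be collected and SPSS fits the model.

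### A normality pre-test decides whether two-year rotation is compared by means or by ranks, and no between-group difference in degrees with an interval is planned

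*Combined protocol and SAP*

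**What the plan says.** The Data Analysis section sets a two-step rule. First, "Before comparing continuous variables, data sets will be assessed for normality using a Shapiro-Wilk Test". Then the result selects the comparison: "For normal data, an independent student's t-test will be used to compare means", whereas "A Mann-Whitney Rank Sum Test will be used for data that is ordinal or not normally distributed". The descriptive summary switches with it: "means and standard deviations if normally distributed, median and range if not normally distributed". On interval estimates the section says "Confidence intervals for the means/medians for each of the two groups will also be computed"; it plans none for the difference between groups. Absolute postoperative values and changes from baseline are both to be compared.

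The Objective section makes external and internal rotation at two years the primary question, and the Physical Evaluation section has rotation measured by goniometer. The Sample Size section works in degrees throughout. It takes a minimal clinically important difference of 14° to 22° and an SD between 8° and 18°, and concludes that with 35 per group "we would be able to detect between 5.4° and 12.2° difference, which will be sufficient to detect a clinically important difference".

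**The concern.** The trial was sized to detect a difference in mean degrees, and its clinical benchmark is also in degrees. The t-test addresses that quantity. The Mann-Whitney test addresses rank order, and as planned it yields a p-value with no accompanying estimate of the difference. Which of the two answers the primary question is settled by a preliminary significance test on the trial's own data.

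Three things follow:

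- If the rank branch is taken, the report need contain no between-group estimate or interval to set beside 14° to 22°.
- The branch can differ between external and internal rotation, between the four postoperative visits, and between change and absolute values of one measurement. That is 2 × 4 × 2 = 16 rotation comparisons, 4 of them at two years. Results bearing on one hypothesis may then be on different footings.
- The section does not say whether Shapiro-Wilk is applied to each arm or to both together, so even the selection rule is open to more than one reading.

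At stake is whether the trial can state how many degrees separate the two versions, and how precisely.

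**Working it through.** **Inputs.** From Sample Size: "We used 80% power and a significance level of 0.05", effect size d = 0.68, 35 per group, SD 8° or 18°, benchmark 14° to 22°. From Data Analysis: the two-step rule, and a 0.05 threshold for all tests, taken here to apply to Shapiro-Wilk without Bonferroni. Assumed, because the documents do not give them: two-sided tests, the recording unit of the goniometer readings, and the shape of any skew.

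**1. The plan's own figure.** The normal approximation gives n per group = 2(1.960 + 0.842)² / 0.68² = 33.9, so 34. The noncentral t calculation gives 34.94, so 35 per group and 70 in total, with power 80.1% at n = 35. Detectable differences are 0.68 × 8 = 5.4° and 0.68 × 18 = 12.2°. Both figures reproduce, and they reproduce as a t-test of means. The sample size is not in question.

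**2. How often normal data go to ranks.** If each arm is tested at 0.05 and both are truly normal, the chance that at least one fails is 1 − 0.95² = 9.75%. Simulation with 35 per group gave 9.5% to 10.0%. If the arms are pooled and do not differ, it is about 5%. If readings are rounded to 5°, the each-arm figure is about 70% at SD 8° and about 17% at SD 18°, because Shapiro-Wilk reacts to tied, coarse values.

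**3. What that does to error rates.** Simulated, 35 per group, Shapiro-Wilk on each arm:

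| Data | Type I error, two-step rule | Power at 0.68 SD, t-test | Power at 0.68 SD, two-step rule |
|---|---|---|---|
| Normal, unrounded | 5.0–5.2% | about 80% | about 80% |
| Normal, rounded to 5° | 5.0–5.1% | 79–81% | 78–80% |
| Moderate skew, same in both arms (gamma, shape 4) | 5.4–5.5% | 79–80% | 84–85% |
| Strong skew, same in both arms (gamma, shape 2) | about 5% | about 80% | about 90% |

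Using Mann-Whitney for every comparison on normal data gives 77.5% to 78.1%, so the loss against 80.1% is 2.0 to 2.6 points. Restoring it would take 34.94 / 0.955 = 36.6, or 37 per group. At a true difference of 14° with SD 18°, power is 89.4% by t-test and about 87.9% by Mann-Whitney.

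**4. When the branches disagree.** They part company when the arms differ in spread or shape. With strongly left-skewed data and equal means, the two-step rule rejects about 5% of the time with equal SDs, about 7% with SDs 14° v 18°, and 10–11% with SDs 12° v 18°. Welch's test stays at about 5%.

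**5. The t-test branch.** Student's version assumes equal variances. With SDs 18° v 8° and 70 completers, its type I error is about 8% if the larger SD is in the smaller arm (30 v 40), about 3% if it is in the larger arm (40 v 30), and about 5% at 35 v 35. The direction depends on the imbalance, and allocation here is 1:1.

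**The case against.** The strongest reply is that choosing a test by normality is a familiar convention and that here it does little harm. Much of that stands. Even if 70% of comparisons are diverted by rounding, the error rates barely move. Under skew shared by both arms the rank test is the more powerful of the two. Group means or medians in degrees will still be reported, each with an interval, so it would be wrong to say that the results could not be compared at all with 14° to 22°. What the reply does not supply is an interval for the difference, or a single method fixed in advance for the primary question.

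A reader might go further and infer that the rule inflates false positives or undermines the sample size. Scenarios can be built to show it. With left skew, equal means and SDs of 8° v 18°, the two-step rule rejects 18% of the time. If 20% of one arm does 40° worse, it detects the 8° mean difference 30% of the time, against 67% for a comparison of means. The documents do not support treating these as expected. The Sample Size section gives 8° to 18° as uncertainty about one common SD, and Table I uses one SD per calculation. Nothing says that the arms will differ in spread by a factor of 18 / 8 = 2.25, or that one arm will contain a subgroup with poor outcomes.

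**Conclusion.** The point holds as a weakness in what is estimated and reported; it is not a failure of error control. The method for the primary outcome is chosen by the data and can vary across related comparisons. On the rank branch, no between-group estimate or interval in degrees is planned.

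The size depends on the recording unit. About 10% of normal comparisons go to ranks if each arm is tested without rounding. With 5° rounding the figure is about 17% (SD 18°) to 70% (SD 8°). The cost in type I error is negligible on normal or equally skewed data, and the cost in power on normal data is at most 2 to 3 points. Materially different conclusions arise only if the arms differ in spread or shape, which cannot be known in advance. Confidence is high about the gap in the wording and lower about how often it would matter, because the rounding unit and the skewed distributions are assumptions. The change is worth making because it is cheap.

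**What to change.** In the Data Analysis section, replace the selection rule for the primary outcomes with wording such as:

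*External and internal rotation in degrees at two years will be compared between groups as a difference in means with a 95% confidence interval (Welch t-test), whatever the result of any normality test. A Mann-Whitney test with a Hodges-Lehmann estimate will be reported as a sensitivity analysis and will not replace the main result. Mann-Whitney remains the main test for truly ordinal items.*

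The hand-position categories on the Appendix A form are an example of the last group. Where change and absolute values of rotation are both compared, use the same method for both.

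The cost is one paragraph and no new data, and power on normal data stays at the planned 80%. The downside is some loss of power against ranks if the data are skewed or heavy-tailed: about 80% against 90% at a 0.68 SD shift under strong skew common to both arms. The sensitivity analysis would show whether that had happened.
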